10.8.3. Laboratory Variables

The following haematology and chemistry (including Liver Function) parameters will be included within data presentations (and presented in the units as shown):

- Haematology: Haemoglobin (g/L), White Cell Count ($10^{**9}/L$), Platelets ($10^{**9}/L$), Haematocrit (L/L), Red Cell Count ($10^{**12}/L$), Mean Cell Volume (fl), Mean Cell Hgb (pg), Mean Cell Hgb Concentration (g/L), Neutrophils ($10^{**9}/L$), Lymphocytes ($10^{**9}/L$), Monocytes ($10^{**9}/L$), Eosinophils ($10^{**9}/L$), Basophils ($10^{**9}/L$), APTT (secs), Fibrinogen (g/L), PT (secs), INR.
- Chemistry (including Liver Function): Sodium (mmol/L), Potassium (mmol/L), Urea (umol/L), Creatinine (umol/L), Total Bilirubin (umol/L), ALT (IU/L), AST (IU/L), Gamma GT (IU/L), Alkaline Phosphatase (IU/L) and Albumin (g/L).

Any other laboratory parameters collected as part of the study (including urinalysis) will only be included in listings. Laboratory data collected in different units to that shown will be converted to the above specified units (if possible) and both will be shown in the listings.

Toxicity grades will be calculated for relevant laboratory parameters, as per Appendix 1 of the study protocol (Section 15.1**Error! Reference source not found.**). Shift tables will be presented showing

changes in each toxicity grade from the baseline grade to the maximum post-baseline grade for each treatment group.

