3.1.2 *Study Methodology*

Participants will be screened in the period Day -42 to Day -1. Informed consent will be obtained before any study specific procedures are performed. Eligible participants will then attend the clinic to receive study vaccine on Day 0. Participants will be enrolled sequentially.

The study will investigate response to study vaccine as shown in [Table 2](#). On Day 0, an electronic diary (eDiary), tape measure and thermometer will be provided to perform self-assessment of local and systemic reactogenicity. All participants will then have a follow-up telephone call on Day 1 and return to the clinic for study assessments on Days 7, 14, 28, 84. Participants in cohorts 1-4 only, will also have follow up visits on Day 56 and Day 168. End of study visit procedures will be performed at the final visit.

Five healthy participants will be administered the low dose first (cohort 1). Dose escalation will only be initiated in the next 5 healthy participants (cohort 2) following SMC review.

Six CHB participants will be administered the low dose (cohort 3) before the dose escalation is initiated in the remaining 6 CHB participants (cohort 4).

Thirty healthy participants (15 who have received two doses of AZD1222 [cohort 5] and 15 who have received at least two doses of either Pfizer or Moderna mRNA COVID-19 vaccine [cohort 6]) will be dosed in parallel with the high dose used in cohorts 2 and 4.

The first participant in each of cohorts 1-4 will be assessed for 1 hour in the clinic post-vaccination in case of immediate adverse events (timed after the end of study vaccine administration). All other participants will be assessed for 30 minutes.

The safety and immunogenicity assessments to be performed in cohorts 1-4 are:

- Haematology (full blood count, haemoglobin, haematocrit, erythrocytes, mean cell volume, mean corpuscular haemoglobin, mean corpuscular haemoglobin concentration, leukocytes, neutrophils, lymphocytes, monocytes, eosinophils, basophils, fibrinogen, prothrombin time [PT] and international normalised ratio [INR], activated partial thromboplastin time [aPTT] and platelets) will be analysed at screening, pre-vaccination on Day 0 and on Days 7, 14, 28, 56, 84 and 168
- Biochemistry (sodium, potassium, urea, creatinine and albumin) will be analysed at screening, pre-vaccination on Day 0 and on Days 7, 14, 28, 56, 84 and 168

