- Liver function tests (LFTs; alkaline phosphatase [ALP], gamma-glutamyl transpeptidase [GGT], alanine transaminase [ALT], aspartate transaminase [AST] and

total bilirubin) will be analysed at screening, pre-vaccination on Day 0 and on Days 7, 14, 28, 56, 84 and 168

- HBV disease markers in serum:
 - Healthy participants: qualitative HBsAg will be tested at screening, hepatitis B surface antibody (HBsAb) and HBcAb will be tested at Day 0, and repeated at the end of the trial if negative at baseline, or at discretion of the Investigator
 - CHB participants: HBV DNA and quantitative HBsAg will be tested at screening and repeated on Days 0, 28, 56, 84 and 168. The following parameters will also be analysed on days 0, 28, 56, 84 and 168: HBeAg, HBcAg, anti-HBs, anti-HBe, anti-HBc, pgRNA
- A full physical examination will be performed at screening and pre-vaccination on Day 0. A symptom-directed physical examination will be performed on Days 7, 14, 28, 56, 84 and 168
- Vital signs will be performed at screening, pre-vaccination and post-vaccination at the on Day 0 and on Days 7, 14, 28, 56, 84 and 168
- Local and systemic reactogenicity (pain, induration, warmth, erythema at the vaccination site plus feverishness, chills, myalgia, fatigue, headache, nausea, arthralgia, malaise) will be captured pre-vaccination and post-vaccination on Day 0 and by eDiary for 3 days post-vaccination
- Unsolicited adverse events will be recorded in the eCRF from the date the informed consent is signed, at all clinic visits to cover the period since the previous visit and during the visit and up to 28 days post-vaccination
- Serious adverse events (SAEs) and adverse events of special interest (AESIs) will be recorded from the date the informed consent is signed until the end of the study and or resolved or until participant contact discontinues
- Cellular immune responses will be measured in peripheral blood mononuclear cells (PBMCs) samples taken on pre-vaccination on Day 0 and on Days 14, 28, 56, 84 and 168. Samples will be analysed by ICS

For participants in cohorts 5 and 6, all assessments on Days 0, 7, 14, 28 and 84 above will be performed. In addition, neutralising antibodies to ChadOx1 will be assessed on Days 0 and 84.

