10.2.2.6.2 Laboratory Safety Tests

Severity grading using the toxicity table in [Appendix 1](#) will be assigned to laboratory safety values where applicable. Laboratory results in reported units and standard international (SI) units will be listed, including high and low flags, severity grades where applicable, the corresponding normal range and clinical significance.

Laboratory safety tests summaries will be based on results in SI units. Absolute and change from baseline results, including the worst change for each variable for each participant will be summarised using descriptive statistics.

Treatment emergent out of range results with the corresponding severity grade, normal ranges, baseline results and clinical significance will be separately listed. Shift tables will be used to show changes from baseline at each timepoint and the worst change in each participant and scatterplots of the worst change will be produced. The number of participants showing shifts of at least two severity grades will be summarised.

The number of participants with treatment emergent clinically significant laboratory safety test results and laboratory safety test results of Grade 3 or 4 will be summarised.

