10. PLANNED STATISTICAL METHODS

10.1. Statistical Considerations

10.1.1. General definitions

Definition of baseline

Baseline is defined as the last non-missing value for a participant, for the particular parameter, that is prior to the administration of study vaccine.

Study completion definition

A participant completes the study by engaging in study activities up to and including the End of Study Visit at Day 168 (+/- 7 days), for cohorts 1 to 4, and Day 84 (+/- 7 days) for cohorts 5 and 6.

Treatment Group

There are six treatment groups in this study; the Healthy Participants and CHB participants are split into high and low doses of vaccination. Healthy participants in the high dose group are further split into those with no previous exposure to ChAdOx1 vectored vaccines, those with recent previous exposure to Covid-19 ChAdOx1 vectored vaccine (cohort 5) and those with previous exposure to Covid-19 mRNA based vaccines (cohort 6).

Results below limit of detection and quantification

Immunogenicity results that are below the limit of quantification or detection (i.e. reported as <X or BLQ) will be replaced by 0 for any summaries but will be listed as reported.

Geometric Mean and Standard Deviation

The geometric mean (GM) and geometric standard deviation (GSD) are obtained by calculating the mean and SD of the log-transformed data and back-transforming these. If there are any zero values in the data a small number should be added to all values before log-transformation and then subtracted from the resulting GM. This small number will be 1 unless stated otherwise.

GM = antilog (mean (log(value + S))) – S, where S is a small number, relative to the non-zero results.

GSD = antilog(standard deviation(log(value + S)))

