10.1.2. Data Presentation

The specific format and content of each data presentation is shown in Section 14.

Summary tables will be presented by treatment group and also for safety summaries, demographic and baseline data, for all participants.

Within all Tables and Figures values for treatment group will be labelled as follows:

- “Healthy Participants – Low Dose”
- “Healthy Participants – High Dose”

- “Healthy Participants: Covid-19 vaccinated – ChAdOx1”
- “Healthy Participants: Covid-19 vaccinated – mRNA”
- “CHB Participants – Low Dose”
- “CHB Participants – High Dose”
- “Total”

For disposition summaries the participants that were screened but not vaccinated with ChAdOx1-HBV may be presented as:

- “Screen Failure”

Within Listings treatment groups will be identified as follows:

- “HP – LD”
- “HP – HD”
- “HP – HD – ChAdOx1”
- “HP – HD – mRNA”
- “CHB – LD”
- “CHB – HD”
- “SF”

And the ordering of treatment groups shown here represent the order they will appear in Tables.

The scheduled protocol visits will be labelled in the report presentations as follows:

- “Screening”
- “Day 0 – pre dose”
- “Day 0 – post dose”
- “Day 1”
- “Day 7”
- “Day 14”
- “Day 28”
- “Day 56”
- “Day 84”
- “Day 168”

Within summary presentations it is envisaged that only scheduled protocol visit values will be used for post-baseline time points. Within the clinical database, a number of data points may be labelled as unscheduled. These data points will be included within participant Listings only. However, at the DRM the occurrence of such non-scheduled data will be reviewed for each participant to decide if (and how) any such data point(s) should be included within summary presentations. Any such decisions will be documented in the DRM minutes.

Where duplicate information is collected (and reconciled) on both the CRF and on the non-CRF vendor data transfer(s) (e.g. sampling date) then only the CRF recorded information will be included in participant listings.

All variables will be listed to the same number of decimal places as reported. Descriptive statistics for all endpoints that are continuous will have the following summary statistics presented in the following order: n, mean (rounded to one more decimal place than recorded), standard deviation (rounded to two more decimal places than recorded), median (rounded to one more decimal place than recorded), minimum (as recorded), and maximum (as recorded).

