Feverishness	n (%)	xx (xx, x)	xx (xx, x)	xx (xx, x)	xx (xx, x)	xx (xx, x)	xx (xx, x)	xx (xx, x)
Chills	n (%)	xx (xx, x)	xx (xx, x)	xx (xx, x)	xx (xx, x)	xx (xx, x)	xx (xx, x)	xx (xx, x)
Joint Ache	n (%)	xx (xx, x)	xx (xx, x)	xx (xx, x)	xx (xx, x)	xx (xx, x)	xx (xx, x)	xx (xx, x)
Malaise	n (%)	xx (xx, x)	xx (xx, x)	xx (xx, x)	xx (xx, x)	xx (xx, x)	xx (xx, x)	xx (xx, x)

The distinct number of participants who experienced reactions of Grade 1 or higher between Day 0 and Day 3 is presented. The reactions on Day 0 are recorded by the investigator, whereas the reactions on Day 1 – Day 3 are recorded by the participant in a diary card. Percentages are based on the number of non-missing observations. All COVID-19 vaccinated participants were given the high dose of ChAdOx1-HBV vaccine.

Table 14.3.4
Shift Summary of Haematology Results by Maximum Toxicity Grade
Safety Analysis Set

Lab Parameter	Baseline Grade [n (%)]	Maximum Post-baseline Grade				Total	Missing
		Grade 0	Grade 1	Grade 2	Grade 3		
Lab Parameter 1							
Grade 0	xx (xx.x)	xx (xx.x)	xx (xx.x)	xx (xx.x)	xx (xx.x)	xx (xx.x)	xx
Grade 1	xx (xx.x)	xx (xx.x)	xx (xx.x)	xx (xx.x)	xx (xx.x)	xx (xx.x)	xx
Grade 2	xx (xx.x)	xx (xx.x)	xx (xx.x)	xx (xx.x)	xx (xx.x)	xx (xx.x)	xx
Grade 3	xx (xx.x)	xx (xx.x)	xx (xx.x)	xx (xx.x)	xx (xx.x)	xx (xx.x)	xx
Grade 4	xx (xx.x)	xx (xx.x)	xx (xx.x)	xx (xx.x)	xx (xx.x)	xx (xx.x)	xx
Total	xx (xx.x)	xx (xx.x)	xx (xx.x)	xx (xx.x)	xx (xx.x)	xx (xx.x)	xx
Missing	xx	xx	xx	xx	xx	xx	xx
Lab Parameter 2							
Grade 0	xx (xx.x)	xx (xx.x)	xx (xx.x)	xx (xx.x)	xx (xx.x)	xx (xx.x)	xx
Grade 1	xx (xx.x)	xx (xx.x)	xx (xx.x)	xx (xx.x)	xx (xx.x)	xx (xx.x)	xx
Grade 2	xx (xx.x)	xx (xx.x)	xx (xx.x)	xx (xx.x)	xx (xx.x)	xx (xx.x)	xx
Grade 3	xx (xx.x)	xx (xx.x)	xx (xx.x)	xx (xx.x)	xx (xx.x)	xx (xx.x)	xx
Grade 4	xx (xx.x)	xx (xx.x)	xx (xx.x)	xx (xx.x)	xx (xx.x)	xx (xx.x)	xx
Total	xx (xx.x)	xx (xx.x)	xx (xx.x)	xx (xx.x)	xx (xx.x)	xx (xx.x)	xx
Missing	xx	xx	xx	xx	xx	xx	xx
...							

Note: Total is the number of subjects with at least 1 post-baseline result, and percentages are based on the row total.
Note: Baseline is defined as the nearest assessment completed prior to vaccination.

Programming note(s):

(1) The table will have separate pages for each cohort, i.e. Healthy Participants high dose, CHB Participants low dose, CHB Participants high dose, Healthy Participants low dose, Healthy Participants - Covid-19 Vaccinated: mRNA.

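### The worst-grade shift tables set no common visit window, so cohorts 1-4 (6 laboratory visits) are not strictly comparable with cohorts 5-6 (4 visits)

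*SAP*

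**What the plan says.** SAP 10.8.3 presents shift tables showing "changes in each toxicity grade from the baseline grade to the maximum post-baseline grade for each treatment group". SAP 10.8.4 repeats this for vital signs. The outputs are Tables 14.3.4 (haematology), 14.3.5 (chemistry) and 14.3.6 (vital signs).

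The visit schedule differs by cohort. Under Protocol 3.1.2, laboratory tests in cohorts 1-4 "will be analysed at screening, pre-vaccination on Day 0 and on Days 7, 14, 28, 56, 84 and 168". For the other two groups the same section says: "For participants in cohorts 5 and 6, all assessments on Days 0, 7, 14, 28 and 84 above will be performed". SAP 10.1.1 defines study completion to match: "up to and including the End of Study Visit at Day 168 (+/- 7 days), for cohorts 1 to 4, and Day 84" for cohorts 5 and 6.

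SAP 10.1.2 envisages that in summaries "only scheduled protocol visit values will be used for post-baseline time points", subject to decisions at the data review meeting. The shell for Table 14.3.4, reused for the other two tables, notes that "Total is the number of subjects with at least 1 post-baseline result, and percentages are based on the row total" and that "The table will have separate pages for each cohort". None of these places sets a common window or allows for the number of visits.

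The protocol had planned more. Its section 10.2.2.6.2 states: "Shift tables will be used to show changes from baseline at each timepoint and the worst change in each participant", and 10.2.2.6.3 plans the same for vital signs. SAP section 11 reduces these presentations because of the low number of participants, and the table list in SAP 13.2 keeps only the maximum-grade shifts.

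**The concern.** A maximum can only stay the same or rise as readings are added. A participant in cohorts 1-4 has two more laboratory visits (Days 56 and 168) at which a grade can be recorded than a participant in cohorts 5-6. Two groups with identical safety at each visit would then be expected to show different worst-grade distributions.

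Cohorts 2, 5 and 6 are all healthy participants given the same dose, and Protocol 3.1.1 waives committee review for cohorts 5-6 because that dose had already been assessed in healthy participants. Setting their shift pages side by side is a natural reading, and 30 of the 35 participants (15 + 15 of 5 + 15 + 15) are on the shorter schedule. By-timepoint shifts would have allowed a like-for-like comparison within the tables. The summary the SAP kept is the one that depends on length of follow-up.

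**Working it through.** The documents state no laboratory abnormality rate, so there is no planned figure to reproduce.

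**Inputs from the documents**
- Post-baseline laboratory visits, cohorts 1-4: Days 7, 14, 28, 56, 84, 168, so k = 6 (Protocol 3.1.2, Table 2).
- Post-baseline laboratory visits, cohorts 5-6: Days 7, 14, 28, 84, so k = 4 (same places).
- Vital signs add the Day 0 post-vaccination reading (Protocol 7.3.4, Table 2), so k = 7 and k = 5.
- Cohort 2 has 5 participants (Protocol Table 1).

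**Inputs assumed, because the documents do not give them**
- p, the chance of a graded value at one visit, taken as equal at all visits and in all cohorts.
- The correlation between visits within a participant.

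**Independent visits.** The chance of at least one graded value in k visits is 1 - (1 - p)^k. At p = 5%:
- six visits: 1 - 0.95^6 = 1 - 0.7351 = 26.5%
- four visits: 1 - 0.95^4 = 1 - 0.8145 = 18.5%
- ratio 0.2649 / 0.1855 = 1.43; difference 7.9 percentage points; times 5 participants = 0.40 of a participant

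| Assumed p | 6 visits | 4 visits | Ratio | Expected gap in 5 people |
|---|---|---|---|---|
| 1% | 5.9% | 3.9% | 1.49 | 0.10 |
| 2% | 11.4% | 7.8% | 1.47 | 0.18 |
| 5% | 26.5% | 18.5% | 1.43 | 0.40 |
| 10% | 46.9% | 34.4% | 1.36 | 0.62 |
| 20% | 73.8% | 59.0% | 1.25 | 0.74 |
| 50% | 98.4% | 93.8% | 1.05 | 0.23 |

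As p tends to 0 the ratio tends to 6/4 = 1.50; as p tends to 1 it tends to 1.00. The largest absolute gap is about 15 percentage points, near p = 20%.

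**Vital signs, p = 5%.** 1 - 0.95^7 = 30.2% against 1 - 0.95^5 = 22.6%, ratio 1.33. The limit for small p is 7/5 = 1.40.

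**Correlated visits.** Under an exchangeable latent-normal model and a beta-binomial model respectively, the relative excess for six against four visits is:
- correlation 0.5: 34% or 17% at p = 2%; 18% or 13% at p = 20%
- correlation 0.9: 16% or 4% at p = 2%; 9% or 3% at p = 20%
- perfect correlation: 0%

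**After the fix.** With Days 7, 14, 28 and 84 in every cohort, k = 4 throughout. At p = 5% with independent visits the figure is 18.5% in all cohorts, ratio 1.00.

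**The case against.** The case for leaving the tables alone is substantial.

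- *The comparisons the documents set out are balanced.* The dose comparisons (cohorts 1 v 2 and 3 v 4) and the COVID-19 vaccine comparison (5 v 6) each have equal visit counts. This stands.
- *No test and no pooling.* Safety is descriptive (SAP 10.8), and the shift tables have one page per cohort with no combined high-dose page. This stands. A reader might infer that the SAP will report a distorted pooled high-dose rate; the shells show no such output.
- *Cohort 2 is tiny.* The expected gap is at most about 0.7 of a participant per parameter, and one event in five has an exact 95% interval of roughly 0.5% to 72%. Cohort 2 is also not randomised against cohorts 5-6 and has a wider age range (18-65 against 40-60 years). This stands, and it caps the importance of the point.
- *Percentages are within baseline-grade rows, not overall rates.* True, but the same formula applies within a row if p is read as the per-visit chance for participants starting at that grade.
- *The listings allow a check by hand.* Listings 16.2.8.1, 16.2.8.2 and 16.2.9 show grades by study day or visit, and SAP section 11 points readers to the listings. True, but a summary should not need reconstruction when a filter would make it comparable.
- *The primary endpoints are elsewhere.* SAP 7.1 lists adverse events, serious adverse events and Grade 3 or higher local and systemic reactions. The laboratory and vital-sign shifts support the primary safety objective but are not among those endpoints.

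**Conclusion.** The point holds, as a minor one. Tables 14.3.4-14.3.6 take a maximum over unequal visit sets. Given equal per-visit rates, the expected worst-grade rate is higher in cohorts 1-4 unless each participant's results are identical across visits. For laboratory tests the relative excess lies above 0% and just under 50%; 43% is an illustration at p = 5% with independent visits, not a prediction.

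A reader might infer a definite inflation, such as 14% to 47%. The documents do not support one: any such range comes from chosen values of p and correlation, and at correlation 0.9 the excess can be as small as 3%. The calculation also assumes that Days 56 and 168 are as likely to show an abnormality as earlier visits; a lower late rate would shrink the excess.

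A reader might also infer that cohort 2 will look more toxic than cohorts 5-6. That is true only in expectation, and by less than one participant per parameter. The contrasts affected are mainly cohort 2, or low-dose cohort 1, read against cohorts 5-6. Cohorts 3-4 have the same visit imbalance against cohorts 5-6 but are a different population.

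**What to change.** In SAP 10.8.3 and 10.8.4 and the shells for Tables 14.3.4-14.3.6:

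1. Tabulate the maximum grade for every cohort over the common visits: Days 7, 14, 28 and 84, plus the Day 0 post-dose reading for vital signs.
2. For cohorts 1-4, keep a further page with the maximum over all visits to Day 168, so that no late abnormality is lost.
3. Name the visit set in each table title.

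Restoring the by-timepoint shifts of Protocol 10.2.2.6.2 and 10.2.2.6.3 would also serve.

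The cost is a visit filter and some extra table pages in a small descriptive study. No new data are needed.

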10.8.4. Vital Signs

Vital signs parameters (temperature (C), pulse rate (bpm), systolic blood pressure (mmHg) and diastolic blood pressure (mmHg)) will be listed.

Toxicity grades will be calculated for relevant vital sign parameters, as per Appendix 1 of the study protocol (Section **Error! Reference source not found.**). Shift tables will be presented showing changes in each toxicity grade from the baseline grade to the maximum post-baseline grade for each treatment group.

10.8.5. Physical Examination

Physical examination results will be listed.

11.CHANGES TO THE PROTOCOL SPECIFIED ANALYSIS DETAILED IN THE STATISTICAL ANALYSIS PLAN

The following changes have been made in the SAP compared to the protocol specified analysis:

- Data Presentations for laboratory parameters, vital signs and physical examination data have been modified to take account of the low number of participants in this study, i.e. fewer types of summary presentations will be produced, and data listings can be referred to for further detail.
- The per-protocol analysis set definition was updated to clarify that only those with major protocol deviations that are judged to impact or bias the analytic results of the study would be excluded.

12. REFERENCES

13. TABLES, FIGURES AND LISTINGS

13.1. Specific Presentation Details

Tables, listings and figures will be provided in a WORD document. All summary tables and figures will have source data footnotes that refer to the relevant listings. Dates will appear as ddmmmyyyy; times as hh:mm, on the 24-hour clock. All listings will be ordered by treatment group, centre, participant number and scheduled visit. For the presentation of summary data, values will be aligned based on the unit column, and not left/right justified. For example:

Parameter	n	xx	xx
Mean	xxx.x	xx.x	
SD	xx.xx	xx.xx	
Median	xxx.x	xx.x	
Min, Max	xx, xx	xx, xx	

All tables, listings and figures will have the SAS program name, output filename and date of production in the footnote.

All tables, listings and figures will include the following study header and footer:

Page x of y

Vaccitech HBV001

Table x.x
Title
analysis set

Source Data: Listing 16.2.x {Source data footnote only appears for tables, where x references relevant listing number}

Program: xxxxxxxxx

Output: xxxxxxx

Date: xxxxxxxxx

